6.4 TREATMENT OF PATIENTS

6.4.1 Treatments Administered

For induction therapy, all patients will receive standard idarubicin + cytarabine chemotherapy. Patients randomized to Groups 2 and 3 will also receive CX-01. CX-01 will be continually infused while idarubicin will be administered per institutional standard.

Group 1: Idarubicin + Cytarabine

- Idarubicin 12 mg/m²/day by slow (10 to 30 minutes) IV injection/infusion daily on Days 1, 2, and 3
- Cytarabine 100 mg/m²/day by continuous 24-hour IV infusion on Days 1-7.

Group 2: Idarubicin + Cytarabine + plus lower dose CX-01

- CX-01 given as a 4 mg/kg initial bolus on Day 1 only, 30 minutes after completion of administration of the first dose of idarubicin, followed by CX-01 0.125 mg/kg/hour as a continuous 24-hour IV infusion on Days 1-7
- Idarubicin 12 mg/m²/day by slow (10 to 30 minutes) IV injection/infusion daily on Days 1, 2, and 3
- Cytarabine 100 mg/m²/day by continuous 24-hour IV infusion on Days 1-7.

Group 3: Idarubicin + Cytarabine + plus higher dose CX-01

- CX-01 given as a 4 mg/kg initial bolus on Day 1 only, 30 minutes after completion of administration of the first dose of idarubicin, followed by CX-01 0.25 mg/kg/hour as a continuous 24-hour IV infusion on Days 1-7
- Idarubicin 12 mg/m²/day by slow (10 to 30 minutes) IV injection/infusion daily on Days 1, 2, and 3
- Cytarabine 100 mg/m²/day by continuous 24-hour IV infusion on Days 1-7.

Re-induction Therapy

A bone marrow aspirate and biopsy will be performed between Days 14-21 of the induction cycle. If bone marrow shows leukemia-free state, i.e. less than 5% blasts in a aspirate sample, no further chemotherapy will be given until recovery of blood counts. If the bone marrow shows more than 5% blasts, a re-induction cycle may be given as outlined above. If the Days 14-21 marrow is indeterminate e.g., if there is a question of residual leukemia, a bone marrow aspirate may be repeated 7 days later for confirmation. Re-induction will be given with the same assigned regimen ("7 + 3" ± CX-01) as

administered during the first induction cycle as outlined above.

If in the Investigator's opinion, the patient is not fit to receive full re-induction cycle of "7 + 3" ± CX-01 at the Investigator's discretion the patient may receive "5 + 2" ± CX-01 which is 5 days of cytarabine and 2 days of idarubicin as outlined below:

Group 1: Idarubicin + Cytarabine

- Idarubicin 12 mg/m²/day by slow (10 to 30 minutes) IV injection/infusion daily on Days 1 and 2
- Cytarabine 100 mg/m²/day by continuous 24-hour IV infusion on Days 1-5.

Group 2: Idarubicin + Cytarabine + plus lower dose CX-01

- CX-01 given as a 4 mg/kg initial bolus on Day 1, 30 minutes after completion of administration of the first dose of idarubicin followed by CX-01 0.125 mg/kg/hour as a continuous 24-hour IV infusion on Days 1-5
- Idarubicin 12 mg/m²/day by slow (10 to 30 minutes) IV injection/infusion daily on Days 1 and 2
- Cytarabine 100 mg/m²/day by continuous 24-hour IV infusion on Days 1-5.

Group 3: Idarubicin + Cytarabine + plus higher dose CX-01

- CX-01 given as a 4 mg/kg initial bolus on Day 1, 30 minutes after completion of administration of the first dose of idarubicin followed by CX-01 0.25 mg/kg/hour as a continuous 24-hour IV infusion on Days 1-5
- Idarubicin 12 mg/m²/day by slow (10 to 30 minutes) IV injection/infusion daily on Days 1 and 2
- Cytarabine 100 mg/m²/day by continuous 24-hour IV infusion on Days 1-5.

Consolidation Therapy

Evaluation for remission will take place at the time of count recovery, or, if no count recovery is achieved, at approximately Day 35 if the patient received one induction course or approximately Day 49 if the patient received re-induction course. Count recovery is defined as ANC >1,000/μL and platelet count of >100,000/μL. Remission will be defined according to IWG criteria (Appendix A). For patients with documented CR, confirmatory bone marrow aspirate slides will be submitted to the Sponsor or designee.

Patients in remission at the end of induction may proceed to consolidation therapy on study, depending upon factors including, but not limited to, European Leukemia Net (ELN) (70) genetic risk and co-existing conditions.

Patients who are not in CR at the end of re-induction will be taken off study and will complete Early Termination Visit as per Table 6—1.

Patients who could benefit from and are eligible to undergo stem cell transplantation will go off the study at any time when transplant is feasible.

Patients will receive up to two cycles of consolidation therapy on study, per NCCN guidelines, depending upon factors including, but not limited to, ELN genetic risk and co-existing conditions. A cycle of consolidation therapy is defined as the time from initiation of chemotherapy on Day 1 until count recovery.

Patients may start consolidation therapy anywhere from 4 to 8 weeks after the start of induction therapy based on treating Investigator judgment. Consolidation will begin no sooner than 28 days from the start of induction therapy.

Subsequent consolidation cycles may begin anywhere from 4 to 8 weeks after the start of the last cycle of consolidation based on treating Investigator judgment.

Patients will receive consolidation therapy in the same treatment group as assigned at randomization, as follows:

Group 1: Cytarabine

- Cytarabine 1.0 gram/m² over 3 hours, every 12 hours on Days 1, 3, and 5.

Group 2: Cytarabine + lower dose CX-01

- CX-01 given as a 4 mg/kg initial bolus on Day 1, 30 minutes after completion of the first 3-hour infusion of cytarabine, followed immediately by CX-01 0.125 mg/kg/hour as a continuous 24-hour IV infusion on Days 1-5 for a total of 120 hours of continuous CX-01 infusion
- Cytarabine 1.0 gram/m² over 3 hours, every 12 hours on Days 1, 3, and 5.

Group 3: Cytarabine + higher dose CX-01

- CX-01 given as a 4 mg/kg initial bolus on Day 1, 30 minutes after completion of the first 3-hour infusion of cytarabine, followed immediately by CX-01 0.25 mg/kg/hour as a continuous 24-hour IV infusion on Days 1-5 for a total of 120 hours of continuous CX-01 infusion
- Cytarabine 1.0 gram/m² over 3 hours, every 12 hours on Days 1, 3, and 5.

6.4.1.1 *Transfusions*

- Red blood cell (RBC) transfusion will be administered according to institutional guidelines
- Platelet transfusions will also be given at the discretion of the treating Investigator based on clinical characteristics and patient need.

6.4.1.2 *Dosing and Method of Administration*

All chemotherapy and CX-01 doses will be calculated based on actual body weight at the beginning of each cycle of induction or consolidation therapy.

Chemotherapy will be administered through a central venous catheter, such as a peripherally inserted central catheter, with two or three independent ports. This catheter may also be used for administration of blood products, IV medications and IV fluids.

CX-01 bolus and continuous infusions may be administered in the same arm through a peripheral IV line; however, must be separate from the central line or port used for chemotherapy.

6.4.1.3 *Preparation of CX-01 Infusion*

The Investigator and pharmacist at the investigational site will ensure Good Pharmacy Practices are followed during the preparation of the CX-01 IV solution. The volumes and CX-01 concentration in the final CX-01 IV solutions must be verified to be correct based on the patient's actual body weight measured at the beginning of the cycle.

6.4.1.4 *Preparation of CX-01 Intravenous Bolus Dose*

The pharmacist will prepare the IV bolus resulting from the 4 mg/kg dose calculation with the amount of CX-01 from the appropriate number of 10 mL vials. Each 1 mL solution contains 50 mg CX-01 and must be further diluted in 0.9% sodium chloride. This calculated volume per patient (based on weight) will be added to 30 mL of 0.9% sodium chloride solution and the total volume administered IV over 5 minutes.

6.4.1.5 *Preparation of CX-01 Continuous Infusion Dose*

The pharmacist will prepare each study treatment solution, adding the calculated amounts of CX-01 and 0.9% sodium chloride to an empty, sterile infusion bag. An IV infusion line will then be attached to the infusion bag, and the infusion set purged with the CX-01 solution. A Luer lock (or similar) will then be placed at the end of the set. As CX-01 doses are weight based, the amount of CX-01 from the vials and saline solution will both vary by patient's weight. Each 1 mL solution contains 50 mg CX-01.

For each continuous infusion bag, an appropriate volume and concentration of CX-01 solution will be prepared such that the patient receives a continuous infusion at the dose

of CX-01 assigned at randomization, 0.125 or 0.25 mg/kg/hour. The final volume of the CX-01 infusion will be 500 to 1000 mL/24 hours. The infusion bags will be prepared at a calculated CX-01 concentration based on the patient's actual body weight.

[figure not shown]
Based upon current stability testing data, CX-01 infusion solutions will expire at room temperature 72 hours after preparation and should be stored in a refrigerator (2 to 8°C) until used.

If the IV infusion is interrupted for any reason, the time of infusion stop will be recorded, along with the reason. The IV infusion will be restarted as soon as possible, and the restart time recorded. The planned cycle days of treatment administration will not be altered, nor will the concentration of the CX-01 solution be adjusted, to compensate for an interrupted CX-01 infusion.

6.4.2 Investigational Product

CX-01 (2-O, 3-O desulfated heparin [ODSH]) is an off-white to pinkish amorphous powder. CX-01 is a low anticoagulant, anti-inflammatory UFH derivative produced for human use compliant with current Good Manufacturing Practices (cGMP). The structural formula for the basic repeating unit that comprises CX-01 is provided in Figure 6—2.

Figure 6—2 Structure of CX-01

Further details are provided in the IB (63).

6.4.2.1 Packaging and Labeling

Idarubicin and cytarabine will be obtained from commercial sources. These treatments will be prepared by the investigational site pharmacy using standard institutional procedures according to the respective package insert for each agent.

Adequate supplies of the study drug, CX-01, will be provided to each investigational site. The study drug (CX-01) was manufactured under cGMP and will be supplied by Sponsor and packaged in 10 mL sterile, single-use glass vials. The 10 mL vial contains 500 mg total CX-01 (50 mg per mL).

Each vial will be labeled in English and in accordance with United States (US)

requirements since all investigational sites participating in the study will be in US. Label text will be approved according to the Sponsor's agreed procedures. The lot numbers and expiration dates of the batches of CX-01 vials used in this study will be printed on the vial labels.

For all vials, a system in accordance with cGMP will be used; ensuring each dose of study drug can be traced back to the respective bulk ware of the ingredients. A complete record of batch numbers and expiry dates of all study drug and labels will be maintained in the Sponsor's study file.

6.4.2.2 *Storage and Stability*

The study medication must be stored in a secure limited access area according to local regulations. CX-01 vials should be stored at room temperature, preferably between 5°C and 25°C (41 F to 77°F).

Long term stability testing for active pharmaceutical ingredient (API) and final product (CX-01 vials) was conducted in compliance with FDA requirements. Results from these stability studies indicate that CX-01 API and CX-01 product are stable for at least 48 months when stored at room temperature. The API and final product studies are being conducted with current production material to confirm prior results and extend the study period to 72 months. A stability study of CX-01 in normal saline diluted for bolus dose concentration and continuous infusion concentration (in polyethylene bags) has confirmed stability of the drug product for at least 72 hours (the maximum period tested) at two concentration levels and at two temperature conditions (2°C to 8°C and room temperature). This testing covers all the ranges for CX-01 concentration/dilution required when dosing for clinical trials.

Since CX-01 vials are photo-stable, there is no need to protect from direct or indirect light.

6.4.2.3 *Study Drug Accountability, Reconciliation, and Return*

Upon completion and termination of the study, all unused and/or partially used study drug must be returned to the Sponsor, or other authorized party if not authorized by the Sponsor to be destroyed at the site.

All study drugs returned to the Sponsor or other authorized party must be accompanied by the appropriate documentation and be clearly identified. Study drug may only be returned after drug accountability is completed. Returned supplies should be in their original containers (vials that have clinical labels attached). Empty vials should not be returned to the Sponsor. Empty vials may not be destroyed until drug accountability is completed. It is the Investigator's responsibility to arrange disposal of all empty vials according to institutional regulations. The return or destruction of unused study drug should be arranged by the site Monitor.

6.4.2.4 *Study Drug Handling and Disposal*

The Sponsor will be responsible for assuring that the quality of the study drug is adequate for the duration of the study. It is the responsibility of the Investigator or designee to ensure that the study drug is only dispensed to the patient. The study drug must be dispensed only from official study sites by authorized personnel according to local regulations. The Investigator or designee must maintain accurate records of the study drug receipt, dispensing information, and disposition.

If study drug is to be destroyed at the site, it is the Investigator or designee's responsibility to ensure that arrangements have been made for the disposal, drug accountability has been completed by the site Monitor, procedures for proper disposal have been established according to applicable regulations, guidelines and institutional procedures, and appropriate records of the disposal have been documented and provided to the Sponsor or designee.

6.4.3 Method of Assigning Patients to CX-01

6.4.3.1 *Patient Identification*

Each newly enrolled patient will be assigned a unique patient identification number using an Interactive Web/Voice Response System (IxRS). Patients will be randomized across all sites. Patients who discontinue from the study will not be replaced.

6.4.4 Selection of Doses in the Study

6.4.4.1 *Selection of Dose*

The selection of CX-01 dose for study in AML has been based upon the dual requirements to have sufficient drug administered to have potential activity but without clinically significant anticoagulation. The study dose chosen (4 mg/kg bolus followed by 0.125 or 0.25 mg/kg/hour for 5 or 7 days) fulfills both of these criteria. In addition, all doses are expected to result in serum levels of CX-01 which are significantly higher than the IC90 identified in preclinical studies for inhibition of CXCL12-CXCR4 interaction.

In a pilot study of CX-01 conducted on 12 patients with newly diagnosed AML, the addition of CX-01 to the traditional "7 + 3" regimen of cytarabine and idarubicin resulted in 11 of 12 patients achieving complete bone marrow remission after the first cycle (92%). It was hypothesized that the increased rate of first cycle induction of remission was from blockade by CX-01 of CXCL12 (SDF-1)/CXCR4-mediated homing of LSC in the marrow niche where they are protected from chemotherapy. The dose and regimen of CX-01 in that trial were well tolerated without associated serious AEs (SAEs). Mean levels of aPTT remained largely in the mid-30 second range.

In a prior study of continually infused CX-01 in patients with metastatic pancreatic cancer (Study PGX-ODSH-2011-PC), CX-01 was administered as an IV bolus loading dose of 4 mg/kg, followed by a continuous infusion of 0.375 mg/kg/hour for 5 days. This

dose was well tolerated and free from major AEs. However, measurement of aPTT in these patients demonstrated that aPTT was increased into the 40 to 45 second range in a limited number of patients. This is a range that is not overtly anticoagulant, but higher than the therapeutic range of aPTT (31.5 to 36 seconds).

Therefore, the chosen dose (4 mg/kg bolus followed by 0.125 or 0.25 mg/kg/hour) represents a rational balance between effective dosing and safety in seriously ill patients with AML.

6.4.4.2 *Dose Modifications*

No dose modification for cytarabine or idarubicin during induction will be allowed. However, dose reduction of cytarabine during consolidation is permitted according to institutional guidelines, or if in the Investigator's opinion the patient cannot tolerate a higher dose.

CX-01 Dose Modifications

- CX-01 will be temporarily discontinued in patients who develop aPTT above 45 seconds during continuous infusion of CX-01 and at least 8 hours after the bolus dose of CX-01, until the aPTT is <35 seconds. CX-01 will then be resumed at a 50% dose reduction. If the aPTT rises above 45 seconds at the reduced dose, CX-01 will be permanently discontinued. If aPTT at the 50% reduced dose is <35 seconds, 4 hours or more after dose reduction, the dose can be escalated by 25%. If the aPTT after dose escalation again rises above 45 seconds at the reduced dose, the CX-01 will be temporarily discontinued until the aPTT is <35 seconds, and then resumed at the previous 50% dose reduction.
- Abnormal liver function:
 - If Grade 1 increases in AST, ALT, or bilirubin occur (e.g., increase in AST or ALT from ULN to 3.0 x ULN; increase in total bilirubin from ULN to 1.5 x ULN), the frequency of liver function testing will be increased, if the Investigator judges that the laboratory abnormalities are potentially related to study treatment. No reduction of dose is required
 - If Grade 2 increases in AST, ALT, or bilirubin occur (e.g., increase in AST or ALT to >3.0 to 5 x ULN; increase in total bilirubin from >1.5 to 3 x ULN), the frequency of liver function testing will be increased to \geq once a week, if the Investigator judges that the laboratory abnormalities are potentially related to study treatment. No reduction of dose is required
 - If Grade 3 increases in AST, ALT, or bilirubin occur (e.g., increase in AST or ALT to >5.0 to 20 x ULN; increase in total bilirubin from >3.0 to 10 x ULN) and if the Investigator judges that the laboratory abnormalities are potentially related to study treatment, study drug must be stopped. Frequent laboratory evaluations (more than once weekly) will be

conducted until liver function tests return to Grade 1 or baseline value. Study treatment will be resumed after liver function tests return to Grade 1 or baseline value provided administration of chemotherapy is in progress. If resumption of study treatment is considered for subjects who have experienced Grade 3 increases in AST, ALT, or bilirubin liver function will be monitored at least daily during CX-01 infusion

- If Grade 4 increases in AST, ALT, or bilirubin occur (e.g., increase in AST or ALT to >20 x ULN; increase in total bilirubin to >10 x ULN) and if the Investigator judges that the laboratory abnormalities are potentially related to study treatment, the patient must discontinue study treatment immediately and will not be re-challenged. The patient will be followed until resolution of abnormal liver function tests.
- Renal function:

If the calculated creatinine clearance drops below 30 mL/min/1.73m² prior to or during dosing with CX-01, the dose of CX-01 will be held until the creatinine clearance rises above 30 mL/min/1.73m².
- For any other Grade 3 or 4 toxicities that appear to be related to CX-01 during either the induction or consolidation cycles, CX-01 will be interrupted until the AE resolves to Grade 1 or less, and then resumed at 0.125 mg/kg/hour provided administration of chemotherapy is in progress. If CX-01 is interrupted for greater than 72 hours, the patient will be discontinued from treatment. If the AE recurs at a level of Grade 3 or higher, the CX-01 will be discontinued.

This study will utilize the National Cancer Institute-Common Terminology Criteria for Adverse Events (NCI-CTCAE) Version 4.03 for AE and SAE reporting. A copy of the CTCAE Version 4.03 can be downloaded: (<http://safetyprofiler.ctep.nci.nih.gov/CTC/CTC.aspx>).

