6.3 Selection of Study Population

6.3.1 Inclusion Criteria

To be eligible to participate in the study, patients must meet the following criteria:

1. Newly diagnosed, *de novo* or secondary, previously untreated AML
2. Age 60 or above
3. Eastern Cooperative Oncology Group (ECOG) performance status of 0 to 2 (Appendix A)
4. Cardiac ejection fraction $\geq 45\%$ (as determined by echocardiography or multi gated acquisition [MUGA] scan)
5. Adequate hepatic and renal function determined by the following laboratory values:
 - Aspartate aminotransferase (AST) or alanine aminotransferase (ALT) $< 2.5 \times$ upper limit of normal (ULN)
 - Bilirubin $< 2.5 \times$ ULN
 - Calculated creatinine clearance by Cockcroft Gault formula > 30 mL/min (see Appendix C).
6. Able to provide informed consent and have signed an approved consent form that conforms to federal and institutional guidelines.

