6.3.2 Exclusion Criteria

Patients who meet any of the following criteria will not be eligible to participate in the study:

1. Patients with acute promyelocytic leukemia based on the presence of t(15;17)(q22;q12) (69) as determined by karyotyping, fluorescence in situ hybridization or polymerase chain reaction
2. Prior chemotherapy for AML (including investigational therapy); prior hydroxyurea to control WBC count and a single intrathecal administration of cytarabine for CNS prophylaxis is allowed
3. Prior intensive chemotherapy or stem cell transplantation for treatment of myelodysplastic syndrome (prior treatment with hypomethylating agents and lenalidomide are allowed)
4. Presence of central nervous system leukemia
5. Presence of significant active infection that is not controlled in the opinion of the Investigator
6. Presence of significant active bleeding
7. History of severe congestive heart failure or other cardiac disease that contraindicates the use of anthracyclines, including idarubicin
8. Pre-existing liver disease (such as CHILD-Pugh Class B or C liver disease; see Appendix D)
9. Renal insufficiency which might adversely affect schedule and dose of therapy with cytarabine as well as management of tumor lysis syndrome.
10. History of drug addiction within the last 6 months
11. Known history of positive Hepatitis B surface antigens
12. Known history of positive test for Human Immunodeficiency Virus antibodies
13. Psychiatric or neurologic conditions that could compromise patient safety or compliance, or interfere with the ability to give proper informed consent
14. History of other active malignant disease within the past 3 years, other than cured basal cell carcinoma of the skin, cured in situ carcinoma of the cervix, or localized prostate cancer that has received definitive therapy. Such prostate cancer patients who are receiving hormonal therapy are eligible
15. Patients receiving any form of anticoagulant therapy (heparin flushes for IV

catheter permitted)

16. Presence of a known bleeding disorder or coagulation abnormality (including but not limited to aPTT >40 seconds) or any condition that requires maintenance of platelet counts at 50,000/ μ L or higher
17. Pregnant or breast feeding patients
18. Patients of childbearing potential not using adequate contraception.

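### The aPTT restart level and the creatinine clearance unit in the CX-01 dose-modification rules do not match the entry limits, and the fixed restart rate is not reconciled with the aPTT reduction rule

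*Protocol*

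**What the plan says.** **Assigned rates.** Protocol Section 6.4.1 gives Group 2 a bolus "followed by CX-01 0.125 mg/kg/hour as a continuous 24-hour IV infusion on Days 1-7" and Group 3 the same bolus "followed by CX-01 0.25 mg/kg/hour as a continuous 24-hour IV infusion on Days 1-7".

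**aPTT.** Exclusion criterion 16 (Section 6.3.2) bars a known bleeding disorder or a "coagulation abnormality (including but not limited to aPTT >40 seconds". Under Section 6.4.4.2, CX-01 is stopped when aPTT exceeds 45 seconds on infusion, at least 8 hours after the bolus, and stays off "until the aPTT is <35 seconds". The text continues: "CX-01 will then be resumed at a 50% dose reduction". Section 6.4.5.2 expects about 35 to 45 seconds during infusion and regards that as clinically unimportant.

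**Renal function.** Inclusion criterion 5 (Section 6.3.1) requires "Calculated creatinine clearance by Cockcroft Gault formula" above 30 mL/min. Appendix C gives that formula without adjustment for body surface area. The hold in Section 6.4.4.2 begins "If the calculated creatinine clearance drops below 30 mL/min/1.73m²", covers the time before as well as during dosing, and lifts once clearance is back above that value.

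**Other related Grade 3 or 4 toxicity.** CX-01 is interrupted until Grade 1 or less "and then resumed at 0.125 mg/kg/hour provided administration of chemotherapy is in progress". No distinction is made between the arms.

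**Link to analysis.** SAP Section 5, item 4, counts failure to follow the dose-modification or stopping rules among the deviations used to define the per-protocol set.

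**The concern.** Hold and restart rules have to work for every patient whom the entry criteria admit. Here two restart or hold limits are set on a different level or scale from the entry limit for the same measurement. A third rule gives a fixed rate, while the aPTT rule works by a proportion of the patient's own rate.

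Two things are at stake. The first is patient safety. Sites following the text literally could withhold CX-01 from patients whom the protocol regards as suitable, fail to hold it in a patient below the entry limit for renal function, or restart a previously reduced patient at a higher rate. The second is the supportive per-protocol analysis. Where a rule can be read in two ways, whether a patient counts as a deviator depends on how the site, or the person classifying deviations, reads it.

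**Working it through.** **Design figure.** The plan's one relevant design figure is the 71.8% power for each dose-versus-control test (Protocol 6.8.1). Exact enumeration of the one-sided Fisher test with 25 per arm, 0.55 against 0.80 and alpha 0.15 gives 71.7%, which agrees. Nothing below enters that calculation.

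**1. aPTT limits side by side (seconds)**

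- Named entry bar: above 40 (6.3.2)
- Hold: above 45 (6.4.4.2)
- Restart: below 35 (6.4.4.2)

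A baseline of 35 to 40 passes the named entry limit. If that patient rises above 45, is held and comes back to baseline, the value is still 35 to 40, so the restart condition is not met. Section 6.4.1.5 does not move the planned cycle days for an interruption, so the lost infusion is not made up. A baseline of 40 or less does not reach the 45-second trigger, so this rule holds nobody on the entry value alone.

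**2. Creatinine clearance**

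If the hold unit is taken literally, its unindexed equivalent is 30 × BSA / 1.73. The documents give no distribution of body surface area (BSA), so the values below are an assumed range.

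| BSA (m²) | Hold limit in mL/min | Compared with entry above 30 mL/min |
|---|---|---|
| 1.5 | 26.0 | 26.0 to 30: below entry limit, not held |
| 1.6 | 27.7 | 27.7 to 30: below entry limit, not held |
| 1.73 | 30.0 | limits coincide |
| 1.8 | 31.2 | 30 to 31.2: eligible, held |
| 2.0 | 34.7 | 30 to 34.7: eligible, held |
| 2.2 | 38.2 | 30 to 38.2: eligible, held |

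An invented example: a man aged 70, 178 cm, 85 kg, creatinine 2.5 mg/dL.

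- Appendix C clearance: (140 − 70) × 85 / (2.5 × 72) = 33.1 mL/min, which meets inclusion criterion 5.
- BSA by the Mosteller formula (listed in SAP 7.5 for drug usage): √(178 × 85 / 3600) = 2.05 m².
- Indexed clearance: 33.1 × 1.73 / 2.05 = 27.9, which is below 30, so CX-01 is held before the first dose.

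**3. Restart rate (mg/kg/hour)**

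| | Group 2 | Group 3 |
|---|---|---|
| Assigned rate | 0.125 | 0.25 |
| Fixed restart / assigned | 0.125 / 0.125 = 100% | 0.125 / 0.25 = 50% |
| Rate after the 50% aPTT cut | 0.0625 | 0.125 |
| Fixed restart / aPTT-reduced rate | 0.125 / 0.0625 = 2.0 | 0.125 / 0.125 = 1.0 |

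The doubling in Group 2 needs an earlier aPTT reduction followed by a separate related Grade 3 or 4 toxicity. Section 6.4.4.2 does not say which rule then governs.

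**The case against.** Several counter-arguments have force.

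- **Restart rate.** A reader might infer that the fixed rate contradicts the arm doses. It does not: 0.125 is one of the two assigned rates, and a single restart level can be applied in both arms. That it leaves Group 2 unreduced is a clinical choice, not an inconsistency. The same bullet carries safeguards: recovery to Grade 1 or less, discontinuation after an interruption of more than 72 hours, and discontinuation if Grade 3 or higher recurs. What stands is the missing link to an earlier aPTT reduction.
- **aPTT.** The 35 to 45 second range in Section 6.4.5.2 applies during infusion, whereas restart is judged with the drug off, so that range alone contradicts nothing. Criterion 16 is not limited to the 40-second figure, and aPTT could fall below baseline. Holds may also be uncommon. Section 6.4.4.1 reports 40 to 45 seconds in only a limited number of patients at 0.375 mg/kg/hour. It also reports means largely in the mid-30s in the AML pilot, which used 6 mg/kg/day, that is 6 / 24 = 0.25 mg/kg/hour. The mismatch for a baseline of 35 to 40 seconds remains.
- **Renal.** Only the unindexed formula is given, so the indexed unit may be a labelling slip. The wording of the hold can be read as a fall from the entry value, and exclusion criterion 9 may remove some borderline patients. Against this, the rule expressly reaches values before dosing.
- **Dose contrast.** A reader might infer that these rules blur a comparison between doses. The trial tests each dose against control in fixed sequence (Protocol 6.8.1, SAP 7.6.1), and the ITT set keeps patients in their randomized arm. No dose-versus-dose test exists to be blurred.

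**Conclusion.** Two mismatches with the entry limits are confirmed, and one gap between rules.

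- The aPTT restart level can leave an eligible patient unable to restart. This applies only with a baseline of 35 to 40 seconds, only after a rise above 45, and on the assumption that aPTT returns to baseline and no lower.
- The clearance unit, read literally, can place an eligible patient on hold before the first dose. This applies only with BSA above 1.73 m² and clearance just above 30 mL/min (30 to 34.7 at an assumed BSA of 2.0). At an assumed BSA of 1.5 the error runs the other way, over 26 to 30 mL/min.
- The fixed restart rate is a secondary point. It raises the rate only for a Group 2 patient already cut to 0.0625, and only if the fixed rate overrides that cut.

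It would be wrong to infer that all three rules produce holds on Day 1 or a failure to restart. Day 1 holds can come only from the renal unit, and failure to restart at the patient's own baseline only from the aPTT level. Whether the 72-hour limit applies to aPTT holds is unclear, because it sits in the bullet on other toxicities. The number of patients affected cannot be derived from the documents, and no power figure or dose-versus-control test changes.

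**What to change.** The sponsor's clinical team should reconcile three sets of passages:

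1. The aPTT entry limit in 6.3.2 with the restart level in 6.4.4.2, taking account of the on-infusion range in 6.4.5.2.
2. The clearance criterion in 6.3.1 and the formula in Appendix C with the renal hold in 6.4.4.2. The text should say whether the same quantity is meant and, if not, how the indexed value is calculated.
3. The restart rate after other toxicity in 6.4.4.2 with the assigned rates in 6.4.1 and with any earlier aPTT reduction, stating which rule prevails.

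No dose, threshold or unit is proposed here. The reconciled wording should be in place before deviations under SAP Section 5, item 4, are classified, so that per-protocol membership rests on one reading. The cost is amendment wording; no new procedure is needed.
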